15.1.1.2 Parameters

- PK parameters for TR, BTZ-043 (M0), M1, M2, M4_{total}, M10 (reported in ICON/PRA TFLs +CSR), defined in table 1
- PK parameters $\Sigma(M0, M1, M2, M4_{total}, M10)$ [reported in ICON/PRA TFLs +CSR]
- PK parameters for 'other metabolites', Σ (parent and all metabolites) as applicable, and defined in table 1 (reported in integrated PK report)

Table 1: Plasma Parameters

Parameter	Description	Analyte	SAS Programming Notes
Cmax	Maximum plasma concentration. Observed peak analyte concentration obtained directly from the experimental data without interpolation, expressed in concentration units	TR, M0, M1, M2, M4 _{total} , and M10	Cmax from WNL
Tmax	Time to maximum plasma concentration. First observed time to reach peak analyte concentration obtained directly from the experimental data without interpolation, expressed in time units.	TR, M0, M1, M2, M4 _{total} , and M10	Tmax from WNL
AUClast	Area under the concentration-time curve (time 0 to time of last quantifiable concentration).	TR, M0, M1, M2, M4 _{total} , and M10, $\Sigma(M0, M1, M2, M4_{total}, M10)$	AUClast from WNL
AUCall	Area under the curve from the time of dosing to the time of the last observation. If the last concentration is positive $AUC_{0-tlast} = AUC_{all}$. Otherwise, AUC_{all} will not be equal to $AUC_{0-tlast}$ as it includes the additional area from the last measurable concentration down to zero or negative observations	TR, M0, M1, M2, M4 _{total} , and M10, $\Sigma(M0, M1, M2, M4_{total}, M10)$	AUCall from WNL
AUCinf	Area under the blood concentration-time curve (time 0 to infinity), calculated as: $AUC_{inf} = AUC_{0-t} + C_{last}/k_{el}$, where C_{last} is the last measurable blood concentration.	TR, M0, M1, M2, M4 _{total} , and M10, $\Sigma(M0, M1, M2, M4_{total}, M10)$	AUCINF_obs from WNL
λ_z (Kel)	Terminal phase rate constant calculated by linear regression of the terminal log-linear portion of the concentration vs. time curve.	TR, M0, M1, M2, M4 _{total} , and M10	Lambda_z from WNL

Parameter	Description	Analyte	SAS Programming Notes
$t_{1/2}$	Terminal phase half-life expressed in time units.	TR, M0, M1, M2, M4 _{total} , and M10	HL_Lambda_z from WNL
AUC _{0-t}	Area under the blood concentration-time curve from time 0 to t hours post-dose.	TR, M0, M1, M2, M4 _{total} , M10 and individual 'other metabolites', $\Sigma(M0, M1, M2, M4_{total}, M10)$, $\Sigma(M0 \text{ and all metabolites})$	n.a. Part of the integrated PK report.
CL/F	Apparent oral clearance, calculated as dose/AUC _{inf}	M0	CL/F from WNL
Vz/F	Apparent volume of distribution at terminal phase	M0	Vz/F from WNL

Note: AUCs will be calculated using linear up / log down, expressed in units of concentration (ng eq/mL) x time (h).

15.1.2 Blood Variables

15.1.2.1 Concentrations

- Individual blood concentrations per time point for TR. Reported in ICON/PRA TFLs + CSR.

15.1.2.2 Parameters

- Individual PK parameters for TR, as defined in table 2

Table 2: Blood Parameters

Parameter	Description	Analyte	SAS Programming Notes
Cmax	Maximum blood concentration of total radioactivity. Observed peak analyte concentration obtained directly from the experimental data	TR	Cmax from WNL

Parameter	Description	Analyte	SAS Programming Notes
	without interpolation, expressed in concentration units		
Tmax	Time to maximum blood total radioactivity concentration. First observed time to reach peak analyte concentration obtained directly from the experimental data without interpolation, expressed in time units.	TR	Tmax from WNL
AUClast	Area under the concentration-time curve (time 0 to time of last quantifiable concentration).	TR	AUClast from WNL
AUCinf	Area under the blood concentration-time curve (time 0 to infinity), calculated as: $AUC_{inf}=AUC_{0-t}+C_{last}/k_{el}$, where Clast is the last measurable blood concentration	TR	AUCINF_obs from WNL
Λ_z (Kel)	Terminal phase rate constant calculated by linear regression of the terminal log-linear portion of the concentration vs. time curve	TR	Lambda_z from WNL
$t_{1/2}$	Terminal phase half-life expressed in time units.	TR	HL_Lambda_z from WNL
AUC0-t	Area under the blood concentration-time curve from time 0 to t hours post-dose.	TR	n.a. Part of the integrated PK report.

15.1.3 Urine Variables

15.1.3.1 Amounts Excreted

- Individual cumulative amount of TR excreted in urine (Ae,urine). Reported in ICON/PRA TFLs + CSR.
 - Calculated as the urine volume times the urine concentration for each day pool and added up per subject.
- Individual cumulative amount of BTZ-043 (M0) excreted in urine (Ae,urine), as measured by LC-MS. Reported in ICON/PRA TFLs + CSR.
 - Calculated as the urine volume times the urine concentration for each day pool and added up per subject.
- Individual cumulative amount of M1, M2, M4_{tot} and M10, excreted in urine (Ae,urine), as measured by LC-MS. Reported in ICON/PRA TFLs + CSR.
 - Calculated as the urine volume times the urine concentration for each day pool and added up per subject.
- Individual cumulative amount of $\Sigma(M0, M1, M2, M4_{total}, M10)$, excreted in urine (Ae,urine). Reported in ICON/PRA TFLs + CSR.
 - Calculated as the urine volume times the urine concentration for each day pool and added up per subject.
- Inter-subject average cumulative amounts of individual 'other metabolites' in urine (Ae,urine), as measured by radio-profiling (see study protocol G-A-MET-21-002). Reported in integrated PK report.

15.1.3.2 Parameters

- PK parameters for TR, BTZ-043 (M0), M1, M2, M4_{total}, M10, and $\Sigma(M0, M1, M2, M4_{total}, M10)$ as applicable, as defined in table 3. Reported in ICON/PRA TFLs + CSR
- PK parameters for 'other metabolites' and $\Sigma(M0$ and all metabolites), as applicable, as defined in table 3. Reported in integrated PK report.

Table 3: Urine Parameters

Parameter	Description	<Analyte	SAS Programming Notes
Aet (urine)	Total amount of drug/metabolites excreted into urine to time t, obtained by adding the amounts excreted over each collection interval per subject.	TR, M0, M1, M2, M4 _{total} , M10 and $\Sigma(M0, M1, M2, M4_{total}, M10)$	Summation t1-tn(Concentration (ng eq/mL)ti-t2*volume(mL)t1-t2)
Aet (urine)	Total amount of drug/metabolites excreted to time t, as obtained from one pool sample across all subjects covering $\geq 90\%$ of TR in urine.	Individual 'other metabolites', $\Sigma(M0$ and all metabolites)	n.a.
Fe (urine)	Fraction (%) of the administered dose excreted into urine $Fe = (Aet \text{ (urine)} / \text{Dose}) * 100$ per subject.	TR, M0, M1, M2, M4 _{total} , M10, $\Sigma(M0, M1, M2, M4_{total}, M10)$	Aet/500 mg*100

Parameter	Description	<Analyte	SAS Programming Notes
Fe (urine)	Fraction (%) of the administered dose excreted into urine Fe = (Aet (urine) / Dose) * 100, across all subjects.	Individual 'other metabolites', $\Sigma(M0 \text{ and all metabolites})$	n.a.
CL _R	Renal clearance of parent drug calculated as Ae/AUCinf	M0	Ae/AUCinf

15.1.4 Feces Variables

15.1.4.1 Amounts Excreted

- Individual cumulative amount of TR excreted in feces (Ae,feces). Reported in ICON/PRA TFLs + CSR.
 - Calculated as the feces homogenate weight times the feces homogenate concentration for each day pool and added up per subject.
- Inter-subject average cumulative amount of BTZ-043 (M0) in feces (Ae,feces), as measured by radio-profiling (see study protocol G-A-MET-21-002). Reported in integrated PK report.
- Inter-subject average cumulative amounts of M1, M2, M4_{total}, M10 and individual 'other metabolites' in feces (Ae,feces, as applicable), as measured by radio-profiling (see study protocol G-A-MET-21-002). Reported in integrated PK report.

15.1.4.2 Parameters

- PK parameters for TR, as applicable, as defined in table 4
- PK parameters for BTZ-043 (M0), and individual metabolites, as applicable, as defined in table 4

Table 4: Feces Parameters

Parameter	Description	<Analyte>	SAS Programming Notes
Aet (feces)	Total amount of radioactivity excreted into feces to time t, obtained by adding the amounts excreted over each collection interval per subject.	TR	Summation t1-tn(Concentration (ng eq/mg)ti- t2*weight(mg)t1-t2)
Aet (feces)	Total amount of drug/metabolites excreted to time t, as obtained from one pool sample across all subjects covering $\geq 90\%$ of TR in feces.	M0, and individual metabolites, $\Sigma(M0 \text{ and all metabolites})$	n.a.
Fe (feces)	Fraction (%) of the administered dose excreted into feces Fe = (Aet (feces) / Dose) * 100.	TR	Aet/500mg*100

Parameter	Description	<Analyte>	SAS Programming Notes
Fe (feces)	Fraction (%) of the administered dose excreted unchanged / as individual metabolites into feces Fe = $(A_{et}(\text{feces}) / \text{Dose}) * 100$ across all subjects and days.	M0 and individual metabolites, $\Sigma(M0 \text{ and all metabolites})$	n.a.

15.1.5 Vomitus Variables

15.1.5.1 Amounts Recovered

- Individual cumulative amount of TR recovered from vomitus ($A_{et}(\text{vomitus})$), if applicable. Reported in ICON/PRA TFLs + CSR.
 - Calculated as the vomitus homogenate volume times the vomitus homogenate concentration for day 1 of each subject.

15.1.5.2 Parameters

- PK parameters for TR as defined in [table 5](#), if applicable. Reported in ICON/PRA TFLs + CSR.

Table 5: Vomitus Parameters

Parameter	Description	<Analyte>	SAS Programming Notes
Aet (vomitus)	Total amount of radioactivity recovered in vomitus to time t on Day 1.	TR	Summation t1-tn(Concentration (ng eq/mg)ti- t2*weight(mg)t1-t2) on Day 1 only
Fe (vomitus)	Fraction (%) of the administered dose recovered from vomitus Fe = $(A_{et}(\text{vomitus}) / \text{Dose}) * 100$, on Day 1.	TR	$A_{et}/500\text{mg} * 100$

15.1.6 Total Excretion Variables

15.1.6.1 Amounts Recovered

- Individual cumulative amount of TR recovered from urine, feces and vomitus ($A_{et, \text{total}}$). Reported in ICON/PRA TFLs + CSR.
 - Calculated as the sum of $A_{e_{\text{urine}}}$, $A_{e_{\text{feces}}}$ and $A_{e_{\text{vomitus}}}$.

15.1.6.2 Parameters

- PK parameters for TR as defined in table 6, if applicable. Reported in ICON/PRA TFLs + CSR.

Table 6: Total Excretion Parameters

Parameter	Description	<Analyte>	SAS Programming Notes
Aet (total)	Total amount of radioactivity excreted in / recovered from urine, feces and vomitus	TR	$Aet \text{ (total)} = Aet \text{ (urine)} + Aet \text{ (feces)} + Aet \text{ (vomitus)}$
Fe (total)	Fraction (%) of the administered dose excreted in / recovered from urine, feces and vomitus $Fe = (Aet \text{ (total)} / \text{Dose}) * 100$.	TR	$Aet \text{ (total)} / 500\text{mg} * 100$

15.2 Pharmacokinetic Summaries

15.2.1 Pharmacokinetic Concentrations

Measured concentrations will be listed and summarized for each sampling time point, analyte and matrix with calculation of arithmetic means, standard deviation and coefficients of variation, as applicable. For inter-subject pooled samples, descriptive statistics will not be provided. Any results below the limit of quantification will be reported as "BLOQ" and samples where no results were obtained will be reported as "NR".

When calculating means for purpose of descriptive statistics and plots, the following rules apply:

- Numeric values > sum of BLOQ & NR → mean will be reported
- Numeric values ≤ sum of BLOQ & NR and NR ≥ BLOQ → NR will be reported
- Numeric values ≤ sum of BLOQ & NR and BLOQ > NR → BLOQ will be reported

Descriptive statistics (number of subjects, arithmetic mean, standard deviation, coefficient of variation) will be used to summarize the plasma concentrations across the 4 subjects at each scheduled time point.

Linear and semi-logarithmic plots of the individual plasma concentration by actual sampling time will be provided per subject for:

- M0, M1, M2, M4_{total}, and M10 (combined in one plot)
- TR in plasma and whole blood (combined in one plot)
- TR, and $\Sigma(M0, M1, M2, M4_{total}, M10)$ (combined in one plot)

In addition, across subject data (arithmetic mean) will be provided for:

- M0, M1, M2, M4_{total}, M10 (combined in one plot)
- TR in plasma and whole blood (combined in one plot)
- TR, and $\Sigma(M0, M1, M2, M4_{total}, M10)$ (combined in one plot)

These plots will show time in hours. Individual plots will use the BLOQ handling procedure described above.

Individual plasma concentration data will be presented together with descriptive statistics.

A separate listing with time deviations and comments will be provided.

For MetID and the integrated PK report:

Concentrations of M0 and metabolites derived from metabolite profiling in Hamilton pool samples of individual subjects will be listed in the MetID and in the integrated PK report for the pooling interval. Plasma exposure of M0 and all metabolites (AUC_{0-t}) and %AUC_{0-t} of TR, M0 and metabolites will be calculated. Descriptive statistics (number of subjects, arithmetic mean, standard deviation) may be used to summarize the plasma concentrations and exposures across the 4 subjects for the pooling interval (if appropriate). The $\Sigma(M0, M1, M2, M3, M4, M10)$ as well as $\Sigma(\text{individual 'other metabolites'})$ may be listed (if appropriate).

15.2.2 Pharmacokinetic Parameters

Pharmacokinetic parameters will be calculated using the software Phoenix WinNonlin 7.0 or higher. TR in plasma and blood will be calculated in version 8.1.

Actual times will be used for the calculation of the parameters. If the actual time or dose time is missing, the scheduled time may be substituted in order to calculate the PK parameters.

The AUC calculation method will be Linear Up Log Down. Pharmacokinetic plasma parameters will be calculated on individual data with group means and relative standard deviation, on pool concentration data or on sum concentration data, as applicable. All parameters will be rounded to three significant figures

before presentation. Plasma concentrations below the limit of quantification (BLOQ) will be handled according to the following rules:

- BLOQ values before the first numeric value will be set to zero.
- BLOQ values after the first numeric value and before t_{max} will be set to missing (i.e. value will be ignored by Phoenix and a linear interpolation will be performed)
- BLOQ values after t_{max} and before the last numeric value will be set to zero (Phoenix will switch from log interpolation to linear interpolation in this case).
- BLOQ values after the last numeric value will be set to zero.

Descriptive statistics (number of subjects, arithmetic mean, standard deviation, coefficient of variation) will be used to summarize the calculated PK parameters. For t_{max} (and t_{last} if applicable), only median will be presented.

According to the Nuvisan SOP BAS_PKM_03, the elimination half-life ($t_{1/2}$) will be calculated using the automatic detection method for profiles with at least 3 numeric data points and a coefficient of determination $r^2 \geq 0.9025$. Where these criteria are not fulfilled, the results will be reported as NC in the result tables.

Parameters based on $\%AUC_{extra}$ above 20% will be flagged but not excluded from descriptive statistics.

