5.0 Study Design

This study is a Phase 1, single-center, open-label study to investigate the absorption, metabolism, and excretion of BTZ-043 after a single oral administration of 500 mg BTZ-043 containing 3.7 MBq of [¹⁴C]BTZ-043 in 4 healthy adult male subjects.

A total of 4 evaluable subjects completing all procedures are required. Six (6) subjects will be enrolled in the cohort in order to have 4 evaluable subjects. If the cohort of 4 subjects administered with 500 mg BTZ-043 containing 3.7 MBq of [¹⁴C]BTZ-043 leads to less than 4 evaluable subjects, the 2 back-up subjects can be dosed subsequently to ensure that 4 subjects have completed all study procedures and are evaluable. If any of the 4 subjects vomits within 4 hours after study drug administration (approximately 2 times the median T_{max} of BTZ-043), the subject will be replaced.

Subjects will be admitted to the clinical research center on Day -1, which is the day prior to Day 1, the day of drug administration.

Subjects will receive a single oral dose of 500 mg BTZ-043 containing 3.7 MBq of [¹⁴C]BTZ-043 on Day 1. Subjects will be discharged from the clinical research center on Day 5 (approximately 96 hours after drug administration) upon satisfactory recovery of radioactivity. If the criteria for discharge are not met on Day 5, subjects will be required to remain confined for a maximum of 3 additional days (Days 6 to 8) until the criteria are met (daily check by quick counts or normal counts, as feasible). The in-house period should be prolonged up to the morning of Day 8 if at least 1 of the following applies:

- Total radioactivity in plasma is higher than 5% of radioactivity- C_{max} and/or PK parameters for determination of the total radioactivity-elimination phase cannot be determined reliably.
- The mass balance in urine and feces is not complete by Day 5 (i.e., <90%).
- The combined urinary and fecal excretion is not $\leq 1\%$ of the administered dose per 24 hours for 2 consecutive days based on ¹⁴C-radioactivity “quick counts” or normal counts, as feasible.

If the criteria for discharge are still not met on Day 8, subjects may be discharged from the clinical site upon discretion of the Investigator. To ensure that adequate consideration is given to the protection of the subject's interests, subjects with an incomplete mass balance on Day 8 will be asked to return to the clinical site for one or two 24-hour visits (Day 11-12 and Day 15-16).

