- b Subjects will be released from the clinic 96 hours after dose administration and upon satisfactory recovery of radioactivity.
- c Complete physical examinations will be conducted at screening, Day -1, and follow-up/early termination. Symptom driven physical examinations may be conducted at any time, per the Investigator's discretion.
- d Sampling of nasal and throat mucosal cells. If deemed necessary, additional tests may be conducted during the study. The nonclinical project manager will be informed immediately upon availability of Day 11 results, as this will qualify the feces samples for metabolite profiling with regard to potential COVID-19 infectivity.
- e Clinical laboratory tests (including clinical chemistry, hematology, and urinalysis): at screening; on Day -1 (admission), Day 2, and Day 4; and at follow-up.
- f 12-lead ECG: at screening; Day -1, and 1 hour, 4 hours, and 24 hours postdose; at discharge; and at follow-up.
- g Vital signs (supine systolic and diastolic blood pressure, pulse, body temperature, and respiratory rate): at screening; at admission; at predose and at 1 hour, 4 hours, and 24 hours postdose; at discharge; and at follow-up.
- h Plasma sampling for PK of BTZ-043 and main metabolites in plasma: at predose and 0.25, 0.5, 1, 1.5, 2, 3, 5, 8, 12, 16, 24, 36, and 48 hours postdose.
- i Total radioactivity in whole blood and plasma: at predose and 0.25, 0.5, 1, 1.5, 2, 3, 5, 8, 12, 16, 24, 36, 48, 72, and 96 hours postdose (in case total radioactivity recovered is still <90%: in addition 120, 144, and 168 hours postdose and at further 24-hour visits [264 and 360 hours postdose] until study completion). Metabolite profiling in plasma: at predose and 0.25, 0.5, 1, 1.5, 2, 3, 5, 8, 12, 16, 24, 36, 48, 72, and 96 hours postdose (in case total radioactivity recovered is still <90%: in addition 120, 144, and 168 hours postdose. Metabolite profiling in plasma: at predose and 0.25, 0.5, 1, 1.5, 2, 3, 5, 8, 12, 16, 24, 36, 48, 72, and 96 hours postdose (in case total radioactivity recovered is still <90%: in addition 120, 144, and 168 hours postdose).

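### Should a below-LLOQ value embedded after tmax be treated as missing, not zero, when AUClast is calculated?

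*SAP*

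**What the plan says.** SAP 15.2.2 gives four BLOQ rules for parameter calculation. Values before the first numeric value and after the last one become zero. Between the first numeric value and tmax, a BLOQ "will be set to missing (i.e. value will be ignored by Phoenix and a linear interpolation will be performed"). After tmax, a BLOQ "and before the last numeric value will be set to zero (Phoenix will switch from log interpolation to linear interpolation in this case"). AUCs use the linear-up/log-down method. AUClast runs to the last quantifiable concentration (SAP 15.1.1.2, Table 1), so an embedded zero lies inside the integral.

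The list is introduced with "Plasma concentrations below the limit of quantification (BLOQ) will be handled according to the following rules", which names plasma only. SAP 15.1.2.2 also plans "Individual PK parameters for TR, as defined in table 2", and that table includes AUClast and AUCinf in whole blood.

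TR sampling becomes sparse late (SAP Appendix 2, note i): "24, 36, 48, 72, and 96 hours postdose", then 120, 144 and 168 h, and 264 and 360 h, if recovery stays below 90%. The only hint of how low the tail is followed is a criterion for prolonging the stay in SAP 5.0: "Total radioactivity in plasma is higher than 5% of radioactivity" Cmax.

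**The concern.** The same pattern gets opposite treatment, and the SAP gives no reason. If radioactivity is measurable both before and after a sample, the level did not fall to zero in between. The zero also replaces log-down integration by two triangles over two adjacent intervals. After 48 h those intervals are 24 h each, so one zero affects 48 h of the curve.

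PK of TR in blood and plasma is a primary objective (SAP 4.1), and only four subjects enter the mean. The safeguards in SAP 15.2.2 do not cover this case. The half-life gate uses the "automatic detection method for profiles with at least 3 numeric data points and a coefficient of determination" of at least 0.9025, and parameters with an extrapolated share "above 20% will be flagged but not excluded from descriptive statistics". Both concern half-life and extrapolation; neither marks an affected AUClast. If the integrated report used the same rule, a low TR AUC would also inflate metabolite shares expressed against it.

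**Working it through.** The plan states no bias figure, so there is none to reproduce. All concentrations, LLOQs, half-lives and CVs below are assumed; the sampling times and integration rules are the SAP's.

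**1. Local example.** Take LLOQ = 10 with 15 at 48 h, BLOQ at 72 h and 10.5 at 96 h.

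- Zero rule: 24 × 15/2 + 24 × 10.5/2 = 180 + 126 = 306.
- Missing: 48 × (15 − 10.5)/ln(15/10.5) = 216/0.3567 = 605.6.
- Reference, if the 72 h value c were known: 24 × (15 − c)/ln(15/c) + 24 × (c + 10.5)/2.

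| True 72 h value c | Reference area | Error, zero | Error, missing |
|---|---|---|---|
| 9.9 | 539.4 | −43% | +12% |
| 8 | 489.3 | −37% | +24% |
| 6.8 | 456.4 | −33% | +33% |
| 5 | 404.5 | −24% | +50% |

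The absolute errors are equal at c = 6.78, about 68% of the LLOQ. Above that, missing is closer; below it, zero is closer. With a steeper preceding drop (30, BLOQ, 10.5, true 9.9) the two are already level: zero gives 360 + 126 = 486, missing gives 48 × 19.5/ln(30/10.5) = 891.6, and the reference is 679.9, so the errors are −29% and +31%.

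**2. Whole-profile AUClast.** First simulation set: absorption 1.5/h, fast half-life 4 h, slow half-life 60 or 100 h, slow share 3, 6 or 10%, lognormal CV 10 or 20%, LLOQ 1% to 5% of Cmax, sampling to 96 h or 168 h. There were 10,000 profiles in each of 120 settings, of which 54 yielded at least 50 profiles with exactly one embedded BLOQ.

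- Mean AUClast error: −0.5% to −8% with zero (low in 54 of 54); +1% to +7% with missing (high in 54 of 54).
- Over the two affected intervals, missing had the smaller mean absolute error in 50 of 54 settings.
- For AUClast itself, missing had the smaller mean absolute error in 15 of 17 settings at CV 10%, but in only 16 of 37 at CV 20%: 31 of 54 overall.

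A second set, also on assumed inputs, had 86 usable settings. Zero was low in 85 of 86, typically by 2% to 8%. Missing was high in all 86, by about 1% to 7%. Missing had the smaller mean absolute AUClast error in 42 of 48 settings at CV 10% to 15% and in 17 of 38 at CV 20%.

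A larger LLOQ widens the gap between the rules. In separate simulations with CV 15%, AUClast under zero relative to missing had a median of about −3% at LLOQ 1% of Cmax, −5% at 2%, −8.5% to −9% at 5%, and −11% to −12% at 10%.

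**3. AUCinf.** AUCinf = AUClast + Clast/λz. Provided the zero is not used in the terminal regression, Clast and λz are the same under both rules. Switching to missing then raises AUCinf by exactly the area added to AUClast (605.6 − 306 = 299.6 in the example). In the first set, the median AUCinf error where reportable was −31% to +11% with zero and −24% to +18% with missing, and missing was higher in 54 of 54. In 24 of those 54, AUCinf was already high under the zero rule, so the switch makes it worse there. In the other 30 the shift may help.

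**4. Frequency and effect on the mean.** Averaged over the first set's settings, the share of profiles with any embedded BLOQ was 0.5% (96 h, CV 10%), 4.2% (96 h, CV 20%), 1.3% (168 h, CV 10%) and 9.0% (168 h, CV 20%). The chance of at least one in four subjects is 1 − (1 − p)^4: 2%, 16%, 5% and 31%. The CV 15% simulations gave under 4% of profiles throughout. With four similar AUCs, one affected subject moves the mean by a quarter of his error: 2%/4 = 0.5%, 4%/4 = 1%, 8%/4 = 2%.

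**5. Visibility.** BLOQ results are reported as such (SAP 15.2.1). Tables 15.2.1.2 and 15.2.1.10 in SAP Appendix 4 show individual TR concentrations and parameters in plasma and whole blood.

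**The case for a change.** The best case for a change is that zero is known to be false while missing is at least plausible, that it biases AUClast low almost without exception, and that missing is closer over the affected intervals in 50 of 54 settings. A narrow rule could be written: a single BLOQ with neighbours no later than 168 h becomes missing, each case is flagged, and both AUCs are reported.

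The direction of the bias stands. The rest carries less weight. Area over two intervals is not a reported parameter, and for AUClast the advantage depends on an unknown CV. The limits on such a rule are also needed. A BLOQ at 264 h between 12 at 168 h and 10.5 at 360 h would be bridged over 192 h, giving 2157 against 1080 with zero. Two BLOQs at 72 and 96 h between 15 at 48 h and 10.5 at 120 h would give 908 against 306. The replacement would therefore treat embedded values differently by count and by time, which repeats the inconsistency it was meant to remove. Flagging and dual reporting would add little with four subjects whose data are already listed.

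The whole-blood wording is a real gap, but a small one. SAP 8.1.2 lists imputation of PK concentrations below the LLOQ without restricting the matrix, and SAP 15.2.2 itself covers TR in plasma and blood. Analysts would apply the same rules to both.

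**Conclusion.** No change is needed. The asymmetry is real and unexplained, and under assumed inputs the zero lowers an affected subject's AUClast by roughly 2% to 8%, or more if the LLOQ is a large fraction of Cmax. Missing exchanges this for an upward error of similar or somewhat smaller size in AUClast and a higher AUCinf, so neither rule is clearly better for the whole profile. The SAP's rule is explicit, was fixed in advance, and states its own effect on interpolation. No hypothesis test depends on it (SAP 8.4.3), and mass balance is calculated under separate rules (SAP 15.2.3). The event is uncommon, the likely shift in a four-subject mean is about 0.5% to 2%, and a reader can see and recompute any affected value. The conclusion would be worth revisiting only if the TR assay proved precise (CV around 10%) and the LLOQ were high relative to Cmax; the documents give neither figure.
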